#### 8.1.1.2. Derived Pharmacokinetic Parameters

Pharmacokinetic parameters will be calculated by standard non-compartmental analysis according to current working practices and using the currently supported version of WinNonlin. All calculations of non-compartmental parameters will be based on actual sampling times. Pharmacokinetic parameters listed will be determined from the prodrug GSK2983559 and active moiety GSK2668176 concentration-time data, as data permits.

Parameter	Parameter Description
AUC(0-t)	Area under the concentration-time curve from time zero to the time of the last quantifiable concentration (C(t)) will be calculated using the linear trapezoidal rule for each incremental trapezoid and the log trapezoidal rule for each decremental trapezoid.
AUC(0-inf)	Area under the concentration-time curve extrapolated to infinity will be calculated as: AUC = AUC(0-t) + C(t) / lambda_z
Cmax	Maximum observed concentration, determined directly from the concentration-time data.
Tmax	Time to reach Cmax, determined directly from the concentration-time data
t1/2	Apparent terminal half-life will be calculated as: t1/2 = ln2 / lambda_z

**NOTES:**

- Additional parameters may be included as required.

**8.1.2. Summary Measures**

- The pharmacokinetic profile following a single dose of GSK2983559
- Derived PK parameters for GSK2983559 and active moiety GSK2668176 including area under the plasma drug concentration versus time curve (AUC(0-t), AUC(0-∞)), maximum observed plasma drug concentration (Cmax), time to maximum observed plasma drug concentration (tmax), and terminal half-life (t1/2) following single (fasted) doses, where data allow.
- Descriptive statistics (n, arithmetic mean, standard deviation [SD] standard error [SE], 95% CI, minimum, median and maximum) will be calculated by treatment for all PK concentrations over time and for the derived PK parameters.
- In addition, for loge-transformed PK parameter variables geometric mean, 95% CI and %CVb (100 \* √(exp(SD) - 1)) will be provided, where the SD is the standard deviation of log-transformed data.

**8.1.3. Population of Interest**

The primary pharmacokinetic analyses will be based on the “Pharmacokinetic” population, unless otherwise specified.

**8.1.4. Strategy for Intercurrent (Post-Randomisation) Events**

- Study completion (i.e. as specified in the protocol) was defined as completing all phases of the study including the follow-up visit.
- Withdrawn participants may be replaced in the study. Replacement participants, enrolled will be dosed with the next planned treatment of the withdrawn participant, and they will not receive any treatment that the withdrawn participant has already received with the exception of the need to increase participants numbers to obtain the minimum number of evaluable participants required for interim decisions, and to obtain data in any other treatment that is required for a valid comparison. Replacement participants will receive the required treatments in the same order as planned for the original participant.

- All available data from participants who were withdrawn from the study will be listed and all available planned data will be included in summary tables and figures, unless otherwise specified.

## **8.2. Secondary Pharmacokinetic Analyses**

### **8.2.1. Endpoint / Variables**

5-ABT and NAc-5-ABT (adjusted to 5-ABT concentration based on molecular weight (MW)) concentrations will be listed, no statistical analysis will be conducted.

#### **8.2.1.1. Drug Concentration Measures**

Refer to [Appendix 5: Data Display Standards & Handling Conventions \(Section 11.5.3 Reporting Standards for Pharmacokinetic\)](#)

### **8.2.2. Summary Measure**

- Listings of 5-ABT and NAc-5-ABT (adjusted to 5-ABT concentration based on molecular weight (MW)) will also be provided

### **8.2.3. Population of Interest**

The secondary pharmacokinetic analyses will be based on the “Pharmacokinetic” population, unless otherwise specified.

## **9. PHARMACODYNAMIC ANALYSES**

### **9.1. Exploratory Pharmacodynamic Analyses**

#### **9.1.1. Endpoint / Variables**

Levels of blood MIP1 $\alpha$ , MIP1 $\beta$  and TNF proteins will be summarised and listed by randomised treatment for Cohort 1 only. No statistical analyses will be conducted.

#### **9.1.2. Summary Measure**

Actual values and percentage change from baseline of blood MIP1 $\alpha$ , MIP1 $\beta$  and TNF proteins will be summarised.

Details of the planned displays are provided in [Appendix 10](#): List of Data Displays and will be based on GSK Data Standards and statistical principles.

Unless otherwise specified, endpoints / variables defined in Section [9.1.1](#) will be summarised using descriptive statistics, graphically presented (where appropriate) and listed.

#### **9.1.3. Population of Interest**

The secondary pharmacodynamics analyses will be based on the “Safety” population, unless otherwise specified.

## **11. APPENDICES**

### **11.1. Appendix 1: Protocol Deviation Management and Definitions for Per Protocol Population**

- Protocol deviations will be tracked by the study team throughout the conduct of the study in accordance with the Protocol Deviation Management Plan.
  - Data will be reviewed prior to freezing the database to ensure all important deviations are captured and categorised on the protocol deviations dataset.
  - This dataset will be the basis for the summaries and listings of protocol deviations.

11.2. Appendix 2: Schedule of Activities

11.2.1. Protocol Defined Schedule of Events

Screening and Follow Up SOA

Procedure	Screening	Follow-up Visit	Notes
	(up to 28 days prior to Day 1)		
Outpatient Visit	X	X	Follow-up Visit to occur approximately 7 days or 5 half lives (as determined from Part A PK data), whichever is longer, and no greater than 14 days after last study drug administration.
Informed Consent	X		
Inclusion and Exclusion Criteria	X		
Medical/medication/drug/alcohol history	X		
Demographics	X		
Full Physical Examination	X		Additional examinations may be performed, or brief examinations made full examinations, by the Investigator, as deemed necessary (e.g. where safety or laboratory findings indicate).
Brief Physical Examination		X	
Drug/alc./cotinine screen	X		Tests include alcohol breath test, urine cotinine and drug screen.
HIV, Hep B and Hep C screen	X		
Tuberculosis Test	X		Conducted as standard practice of the site.
Serum Pregnancy Test (all females)	X		
FSH and estradiol (all females)	X		
Hema/Chem/Urinalysis tests	X	X	
Coagulation Panel	X		
Lipid panel (Part B only)	X		
Height and weight	X		
Holter Monitoring (24-hour)	X		
12-lead ECG	T	X	T= Triplicate
Vital signs	X	X	Vital signs to include heart rate, blood pressure, respiration rate and temperature.
Concomitant Medication Review	X	X	
AE and SAE Review		X	

Part A SOA

Procedure	Study Day (each dosing session)																		Notes		
	Day -1	Day 1 (time relative to dose) See Study Reference Manual for assessment time windows																Day 2	Day 3	Participants to be admitted to the unit the day before dosing (Day -1), and remain in house until discharge after 48-hour post-dose assessments (Day 3) are completed.	
		Pre dose	0 h	15min	30min	1 hr	1.5 hr	2 hr	2.5 hr	3 hr	4hr	5hr	6hr	8 hr	10 hr	12 hr	24 hr	48 hr			
Pregnancy test (all females)	X																				
Brief Physical Examination	X																		X	X	Additional exams./screens may be performed, or brief exams made full exams. by the Investigator, as deemed necessary (e.g. where safety or laboratory findings indicate).
Drug/alc./cotinine screen	X																				Additional assessments may be performed at the discretion of the Investigator. Tests will be conducted within site specified standards.
Heam/Chem/Coags/Urinalysis	X	X																			Non-fasted samples will be collected on Day -1 and at 8 hours on Day 1. Non-fasted chemistry only will be collected at 8 hour time point.
Neuro. examination	X							X											X	X	
Telemetry		<----->																		Continuous at least 8 hours post-dose. Initiate at least 15 min. prior to dosing	
Vital signs	X	T			X		X	X	X		X								X	X	Vital signs to include HR, BP, respiration rate and temperature. T = Triplicate (HR and BP only) single respiration rate and temperature. Timings will be reviewed as cohorts progress and may be adjusted to ensure appropriate measurements relative to peak concentrations for subsequent cohorts.
12-lead ECG	T	T					X	X	X		X								X	X	
Meals	All	D										Per site Schedule									Prior to dosing, participants will fast for 8 hrs overnight; no food is allowed for at least 4 hrs post-dose. Water is permitted with dosing and at all times except 1 hour pre-dose through 2-hours post-dose. Participants will receive standardized meals scheduled at the same time in each period.
	Cohort 2, fed period	D	B																		
Study Treatment dosing					X																A minimum interval of 30 minutes will be observed between the dosing of the first 2 participants at each dose level. A minimum interval of 15 minutes will be observed between the dosing of the remaining 6 participants.
PK Blood Sample		X		X	X	X	X	X	X	X	X	X	X	X	X	X	X	X	X		The number and sampling times may be adjusted once the human PK data are available.
Urine Collection for Metabolites		X	<-----0-24 hours----->																		Participants will void bladder prior to dosing, a sample will be kept as control. 0-24-hr urine samples will be collected.
PD Blood Sample		X								X									X	X	Two samples will be drawn at pre-dose. The PD sampling time points may be updated based on emerging PK data. PD samples will not be collected in the food effect part of the study.
TE Blood Sample		X								X									X	X	TE samples will not be collected in the food effect part of the study
Adverse Event Review		<-----X----->																		See section 10.1.1 for pre-dose SAE requirements	
Concomitant Med.		<-----X----->																			

For ECG and vital signs T=TriPLICATE, For Meals B=Breakfast, D=Dinner

**11.3. Appendix 3: Assessment Windows**

**11.3.1. Definitions of Assessment Windows for Analyses**

No Assessment Windows will be defined for Analysis, and summaries and analyses will be based on nominal visits.

## 11.4. Appendix 4: Study Phases and Treatment Emergent Adverse Events

### 11.4.1. Study Phases

Assessments and events will be classified according to the time of occurrence relative to the start and/or stop date/time of the study treatment within the period for Part A.

Study Phase	Definition
Pre-Treatment	Date < Study Treatment Start Date
On-Treatment	Study Treatment Start Date ≤ Date ≤ Study Treatment Stop Date + 1
Post-Treatment	Date > Study Treatment Stop Date + 1

#### 11.4.1.1. Study Phases for Concomitant Medication

Study Phase	Definition
Prior	If medication end date is not missing and is before 28 days prior to screening visit
Concomitant	Any medication that is not a prior

**NOTES:**

- Please refer to [Appendix 7: Reporting Standards for Missing Data](#) for handling of missing and partial dates for concomitant medication. Use the rules in this table if concomitant medication date is completely missing.

### 11.4.2. Treatment Emergent Flag for Adverse Events

Flag	Definition
Treatment Emergent	
 
• If AE onset date is on or after treatment start date & on or before treatment stop date +1.
 
• Study Treatment Start Date <math>\leq</math> AE Start Date <math>\leq</math> Study Treatment Stop Date + 1
 
• For studies with greater than one treatment period (e.g., crossover study), if AE onset is during one period and worsens during a later period it would be counted in both periods. For the initial period the logic would be as above. For the later period the logic would use the treatment dates associated with the later period:
 
• Treatment Period Start Date <math>\leq</math> AE Worsening Date <math>\leq</math> Study Treatment Stop Date +1 day
 

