### **Treatment period**

- Cohort 1 (single dose) will be comprised of up to 5 study periods, each at least 4 days in duration with participants in-house for 3 nights (through 48 hours post-dose). During each treatment period, participants will be admitted to the unit the day before dosing and will be discharged after completion of the 48-hour post-dose assessments.
- Cohort 2 (single dose) will be comprised of up to 4 study periods, each at least 4 days in duration with participants in-house for 3 nights (through 48 hours post-dose). During each treatment period, participants will be admitted to the unit the day before dosing and will be discharged after completion of the 48-hour post-dose assessments.
- Participants in Cohort 2 (food effect) will participate in up to 2 additional treatment periods and receive a single oral dose of GSK2983559 under fasted (Period 4) and/or fed (Period 5) conditions, dose to be determined by DEC.

If the dose level chosen for the food effect assessment was administered in:

- Cohort 1: participants will receive the dose of open-label GSK2983559 under fasted (Period 4) and fed (Period 5).
- Cohort 2: participants will only receive the dose of open-label GSK2983559 under fed (Period 5) conditions.
- All participants will participate in no more than 5 Treatment Periods (see [Table 5](#) and [Table 6](#)).
- Participants will have a follow-up visit at least 7 days or 5 half-lives whichever is longer, and no greater than 14 days after last dose of GSK2983559. If warranted, additional follow-up visits may be scheduled.

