### **10.1.1. Time Period and Frequency for Collecting AE and SAE Information**

- All SAEs will be collected from the start of treatment until the follow-up visit at the time points specified in the SoA (Section 2). However, any SAEs assessed as related to study participation (e.g., study treatment, protocol-mandated procedures, invasive tests, or change in existing therapy) or related to a GSK product will be recorded from the time a subject consents to participate in the study.
- All AEs will be collected from the start of treatment until the follow-up visit at the time points specified in the SoA (Section 2).
- Medical occurrences that begin before the start of study treatment but after obtaining informed consent will be recorded on the Medical History/Current Medical Conditions section of the case report form (CRF) not the AE section.
- All SAEs will be recorded and reported to the sponsor or designee within 24 hours after becoming aware of the event, as indicated in [Appendix 4](#). The

investigator will submit any updated SAE data to the sponsor within 24 hours of it being available.

- Investigators are not obligated to actively seek AEs or SAEs in former study participants. However, if the investigator learns of any SAE, including a death, at any time after a participant has been discharged from the study, and he/she considers the event to be reasonably related to the study treatment or study participation, the investigator must promptly notify the sponsor.
- The method of recording, evaluating, and assessing causality of AEs and SAEs and the procedures for completing and transmitting SAE reports are provided in [Appendix 4](#).

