### **7.1. Adverse Events Analyses**

Adverse events analyses including the analysis of adverse events (AEs), Serious (SAEs) and other significant AEs will be based on GSK Core Data Standards. The details of the planned displays are provided in [Appendix 10](#): List of Data Displays.

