**NOTES:**

- If the study treatment stop date is missing, then the AE will be considered to be On-Treatment.
- Time of study treatment dosing and start/stop time of AEs should be considered, if collected.

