### 11.6.2. Study Population

Treatment Compliance

 
• Treatment compliance will be calculated based on the formula:  Treatment Compliance = Number of Actual Doses / (Planned Treatment Duration in Days * Frequency) 
 
• Planned Treatment Duration is defined as 1 day in Part A in each period
 

Extent of Exposure

 
• Number of days of exposure to study drug will be calculated based on the formula:  Duration of Exposure in Days = Treatment Stop Date – (Treatment Start Date) + 1 
 
• Participants who were randomised but did not report a treatment start date will be categorised as having zero days of exposure.
 
• The cumulative dose will be based on the formula:  Cumulative Dose = Sum of (Number of Days x Total Daily Dose) 
 
• If there are any treatment breaks during the study, exposure data will be adjusted accordingly.
 

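### The rule for a missing AE stop day caps it at the treatment stop date and can put the stop before onset; the reading of the Part A treatment-emergent window should also be stated

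*SAP*

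**What the plan says.** **Partial dates.** SAP 11.7.2.1 sets conventions for AE dates with a missing day, for use in time to onset and duration. A missing stop day becomes the last day of the month. If that falls after the stop date of study treatment, the treatment stop date replaces it. Nothing compares the result with AE onset. Listings show partial dates as recorded.

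**Length of treatment.** SAP 11.6.2: "Planned Treatment Duration is defined as 1 day in Part A in each period".

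**Treatment-emergent flag.** SAP 11.4.2 requires onset on or after treatment start and "on or before treatment stop date +1". SAP 11.4.1 classifies events relative to the start or "stop date/time of the study treatment within the period for Part A". The notes to 11.4.2 add: "Time of study treatment dosing and start/stop time of AEs should be considered, if collected".

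**AE collection.** Protocol 10.1.1: "All AEs will be collected from the start of treatment until the follow-up visit". The schedule in SAP 11.2.1 places follow-up "no greater than 14 days after last study drug administration". Protocol 5.1 describes the study periods as "each at least 4 days in duration with participants in-house for 3 nights (through 48 hours post-dose".

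**Standards.** SAP 7.1 says that analyses of AEs, serious AEs and "other significant AEs will be based on GSK Core Data Standards". SAP 11.5.1 builds the analysis datasets to the sponsor's data standards. Neither set of standards is in the documents.

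**The concern.** An AE can outlast treatment, and after a single dose it usually will if it lasts into another day. Capping its stop date at the treatment stop date therefore has no logical basis in Part A. The result can contradict two recorded facts: the onset date and the stop month. A duration of zero or less is impossible, and the rule exists to calculate durations.

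The flag raises a smaller question. Safety and tolerability is the primary endpoint, and in a crossover each AE has to be tied to a dose. A window that closes on Day 2 ends before the 48-hour in-house assessments and well before follow-up. The SAP does not say which displays use the flag, or to which dose an AE belongs if it starts between discharge and the next dose.

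**Working it through.** The plan gives no figure to reproduce. The check is date arithmetic on its own rules.

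**A. Treatment stop date in Part A.** SAP 11.6.2 defines exposure as stop date - start date + 1. Setting this to 1 day gives stop date = start date = dose date. The study-day convention in SAP 11.6.1 makes that Day 1.

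**B. Imputed stop date.** Imputed stop = the earlier of (last day of the stop month) and (treatment stop date). The SAP gives no formula for AE duration, so both common forms are shown: stop - onset + 1, then stop - onset in brackets. All dates are illustrative.

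*Per-period reading, dose 14 March, stop recorded as March with no day.* Month end, 31 March, is after 14 March, so the stop is set to 14 March.
- Onset 14 March: 14 - 14 + 1 = 1 day (0). No inversion.
- Onset 15 March: 14 - 15 + 1 = 0 (-1).
- Onset 20 March: 14 - 20 + 1 = -5 (-6).

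The inversion is general. For any onset after the dose day, stop-month end >= onset > dose date, so the cap always applies and the imputed stop (the dose date) always precedes onset.

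*Study-level reading, doses 14 and 28 March, the second being the last.*
- Onset 15 March, stop in March: stop 28 March, duration 28 - 15 + 1 = 14 days. No inversion.
- Onset 29 March, stop in March: stop 28 March, duration 28 - 29 + 1 = 0 (-1).

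*Either reading.* Onset 14 March, stop recorded as April with no day: the stop becomes 14 March (per period) or 28 March (study level). Both fall before the recorded stop month.

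**C. Treatment-emergent window.** Per period, stop date + 1 = Day 2, so onsets on Days 1 and 2 are emergent and those from Day 3 are not. The exceptions are an AE that worsens inside a later window, a missing treatment stop date, and a partial start date imputed to treatment start. If the treatment dates in 11.4.2 are instead read across the whole study, only onsets two or more days after the last dose are non-emergent.

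Share of AE-collection days inside the window after the last dose:
- follow-up at 7 days (Days 1 to 8): 2/8 = 25%
- follow-up at 14 days (Days 1 to 15): 2/15 = 13%

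These are shares of days, not of AEs; the documents do not give onset timing.

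Length against the observed half-life of about 8 h (Protocol 5.5.4, dose selection for Part B):
- On dates, with dosing assumed between 12:00 and 06:00, Day 2 ends 36 to 42 h post-dose: 36/8 = 4.5 to 42/8 = 5.25 half-lives, and 12 to 6 h before the 48 h assessments.
- If clock times turn the extra day into 24 h: 24/8 = 3 half-lives, and 24 h before them.

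**The case against.** **On the stop date.** No planned table is titled for AE duration, listings keep the recorded partial date, and neither counts nor the flag depend on the imputed stop. The cap refers to the stop date of study treatment, which could mean the last dose in the study; inversion then needs both a missing stop day and an onset after that dose. All of this stands and limits the reach of the error. It does not rescue the rule, which fails on either reading and in the one calculation it is written for. Unseen standards do not cure it, because the fault is in the SAP text itself.

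**On the window.** A reader might infer that late AEs drop out of the safety tables. The documents do not show this. SAP 11.10.5 and 11.10.11 title the main AE displays as covering all AEs, and no AE table or listing there is shown to filter on the flag. A reader might also infer that late AEs belong to no dose. That goes too far as well: 11.4.2 already presupposes that AEs are assigned to periods, SAP 11.5.2 reports by actual treatment received, and the sponsor's standards may contain the rule. What stands is that the text gives no period end and no stated rule.

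Nor do the documents show that the window is too short. On dates it covers roughly five observed half-lives. Protocol 5.4 predicts three days to the assay's quantification limit at the highest selected dose, but that concerns detectability and rests on an estimated 5-hour half-life. Finally, 11.4.2 mixes period and study-treatment dates in one condition. SAP 11.4.1 favours the per-period reading but does not exclude the other.

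**Conclusion.** The stop-day rule in SAP 11.7.2.1 is wrong as written. Per period, it puts the stop before onset for every AE that starts after the dose day and lacks a stop day; at study level, for such AEs starting after the last dose. On both readings it overrides a recorded stop month later than the month of treatment stop. The damage is confined to derived AE durations. How many AEs are affected cannot be known from the documents, because the frequency of missing stop days is not given.

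The treatment-emergent window is a secondary, minor matter. On the per-period reading, AEs with onset on Day 3 or later are flagged non-emergent apart from the narrow exceptions above; at study level, only those starting two or more days after the last dose. An effect on any planned AE table or listing is not shown. The gap is one of specification: which reading applies, which displays use the flag, and how late AEs are tied to a dose. A different window would be a choice of convention, not a required correction.

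**What to change.** **SAP 11.7.2.1 (should be corrected).** Remove the cap at the treatment stop date. Impute a missing AE stop day as the last day of the recorded stop month, or as the last contact date if that lies within the month. Never impute before AE onset or before the recorded stop month. Do not use the follow-up visit as a new cap, because Protocol 10.1.3 follows serious AEs until they resolve or stabilise. The cost is a sentence of SAP text and one small derivation. Month end may still overstate a duration, but it is already the rule's starting point.

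**SAP 11.4.2 (clarification).** State whether treatment dates are per period or study level, name the displays that use the flag, and either write the attribution rule or cite the standard that sets it. One possible rule assigns each AE to the most recent dose, until the next dose or, after the last dose received, until follow-up. The cost is wording only.

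Extending the emergent window to the same limits is optional. It would credit some unrelated late AEs to a dose, and a delayed effect could be counted under the next treatment, possibly placebo. If it is adopted, the SAP should say so.
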